6. ANALYSIS POPULATIONS

The Genetic Analysis Population will consist of subjects enrolled in clinical studies VEG102616, VEG105192 and VEG107769 who provided written informed consent for genetics research, provided a blood sample for genotyping and were successfully genotyped for at least one of the genetic markers under study, have valid phenotype data and pass subject QC as described in Section 10.1.2.

7. GENERAL CONSIDERATIONS FOR DATA ANALYSES

It is anticipated that after an initial review of the results of the analyses described here, there may be need for additional follow-up analyses to be conducted. These will be discussed, defined, and agreed by the authors of this RAP and other relevant parties at that time. In that case, there will be no formal amendments to this RAP; any additional follow-up analyses will be described in the Genetic Study report/synopsis.

7.1. Dependent Variable (Endpoint Variable)

The dependent variables will:

- Diarrhoea case-control status, and (as defined in Section 2.2).
- Diarrhoea toxicity levels (defined an ordinal categorical variable).

7.2. Independent Variables

The following variables will be assessed for inclusion as covariates whilst testing for genotype effects.

- Study
- Gender (M/F)
- Age (yrs)
- Baseline body mass index (BMI)
- Baseline patients performance status, ECOG score
- Baseline neutrophil count
- Ethnicity/Ancestry information derived as outlined in Section 10.4

7.3. Genetic Markers

7.3.1. Candidate Genes and Genetic Markers

Thirty-eight candidate genes were selected for inclusion in this investigation (Table 7-1). These include genes that are involved in the pharmacokinetic and pharmacodynamic pathway of pazopanib, or may be related to the presumed mechanism of diarrhoea. 1380 SNPs including 53 functional genetic markers, which map to these genes, will be evaluated. For detailed information of the candidate genes and markers, see Appendix (section 13.1).

Group	Gene Name	Number of genes
Pazopanib ADME	CYP3A4/5	6
	CYP2C8	
	NR1I2	
	ABCB1	
	ABCG2	
Pazopanib mode of action	VEGFR1/2/3	7
	PDGFR α / β	
	c-kit	
	VEGFA	
Diarrhoea	SLC6A4 (5-HT)	25
	CFTR	
	CLCA1	
	SLC12A2	
	ATP1A1	
	ADCY3 / ADCY6	
	NOS3	
	SLC9A3	
	SLC5A1	
	SLC26A3	
	SCNN1A / SCNN1B / SCNN1G	
	ANO1	
	TNF	
	IFNG	
	IL1B/4/6/8/10/12A/12B/13	
Total		38

Table 7-1 Diarrhoea Candidate Genes List

7.3.2. Genetic Markers from GWAS

In addition to the candidate gene markers, analysis will be performed using the rest of genetic markers from Illumina Human1M DNA Analysis Beadchip.

7.4. Marker Map

The NCBI 36 map will be used in this analysis

7.5. Examination of Subgroups

No subgroup has been identified at this time for independent analysis.

7.6. Multiple Comparisons and Multiplicity

A set of p-value thresholds will be used to claim significant association. To establish these thresholds, control of the family-wise type I error for multiple tests will be calculated as described below. All genetic markers are categorized into three tiers based on the prior biological information. The first tier includes 53 functional markers from the candidate genes. The second tier consists of the rest of the markers (~1300 SNPs) in the candidate genes. The third tier will comprise all other Illumina 1M markers that do not map to the 38 candidate genes (~1M markers). A family-wise error rate of 0.05 is allocated evenly to the three tiers, that is, 0.0167 (determined from 0.05/3). The

significant p-value thresholds for the first, the second and third tiers are calculated using the Bonferroni correction, which is 0.0167 / (number of markers), for each analysis at each tier. Linkage disequilibrium among markers within each category will be taken into account and an effective number of tests in Tier 1 & 2 can be estimated for the purpose of the multiple test adjustment [Moskvina, 2008]. Once the actual number of markers to be analyzed within each category has been determined, a per-marker significance level will be calculated and applied to the statistical test results.

Genetic markers that satisfy nominal p-value thresholds of ≤ 0.05 , ≤ 0.01 , and $\leq 10^{-4}$ in the first, second and third tiers, respectively, will also be summarized as suggestive evidence for association; which will be further evaluated in future studies.

8. DATA HANDLING CONVENTIONS

8.1. Premature Withdrawal and Missing Data

If a subject is included in the Genetics Analysis Population, as defined in Section 6 then the subject will be included in the analyses outlined here. If a subject withdrew from the study but did not withdraw consent for genetic research, the subject's information will still be used in these analyses.

Missing data will not be imputed in the analysis.

9. STUDY POPULATION

9.1. Disposition of Subjects

The number of subjects in the PGx Analysis Population will be summarized overall and by study.

9.2. Demographic and Baseline Characteristics

Summaries of baseline demographics will be produced as needed. In general, categorical data will be summarized using frequency counts and percents, and continuous data will be summarized using means, standard deviations, minimums, medians, and maximums, overall and by grade of diarrhoea experienced. These summary statistics will be inspected visually for any concerning imbalances.

10. GENETIC ANALYSIS

The Case-Control analyses will be performed on the binary outcome measure (diarrhoea status), using logistic regression analysis; the ordinal data analyses will be performed on ordinal categorical diarrhoea toxicity grade levels, using proportional odds model, if the marker meets the p-value threshold for suggestive evidence in the primary anlaysis. The analysis strategies that will be employed are outlined in this section.

10.1. Data Quality Control

Prior to the genetic association analysis, quality control (QC) will be conducted on the genetic markers themselves and on the subjects utilizing the genetic marker data.

10.1.1. Genotype Quality Control

The objective of genotype QC analysis is to define the genetic markers that are of high quality and suitable for use in genetic association analyses. For this investigation, genotype data will be extracted from the existing data in the previous pazopanib PGx studies [see GlaxoSmithKline Document Number HJ2009/00002/00 and GlaxoSmithKline Document Number RM2008/00332/00].

10.1.2. Subject Quality Control

The subjects for this investigation have been QC'ed previously [see GlaxoSmithKline Document Number HJ2009/00002/00 and GlaxoSmithKline Document Number RM2008/00332/00].

10.2. Hardy-Weinberg Equilibrium (HWE) Analysis

Departure from Hardy-Weinberg equilibrium (HWE) is a measure of the association between two alleles at an individual locus. A diallelic marker locus is in HWE if the frequencies of the genotypes 11, 12 and 22 are p^2 , 2pq and q^2 respectively, where p and q = 1 - p are the frequencies of the alleles 1 and 2 respectively. The expected frequencies of the three genotypes will be obtained from the observed allele frequencies, on the assumption that the locus is in HWE. Significant departure from HWE may indicate a laboratory genotyping error and population genetic imbalance.

HWE analysis will be performed on all markers and will be conducted using the White subjects sub-population. Departure from HWE will be tested using an exact test, by considering the distribution of genotypes conditional on observed allele frequencies. No markers will be removed prior to association analysis based on their HWE P-values. Markers showing substantial evidence of departure from HWE will be investigated thoroughly for potential laboratory errors or other causes of departure from equilibrium and, if the cause remains undetermined, they may be removed from the list of associated markers. Results pertaining to such markers will be interpreted cautiously.

10.3. Linkage Disequilibrium Analysis

Linkage Disequilibrium (LD) analysis will be conducted to measure the association between alleles at different loci. The LD between two markers can be given by $D_{AB} = p_{AB} - p_A p_B$, where p_A is the allele frequency of A allele of the first marker, p_B is the allele frequency of B allele of the second marker, and p_{AB} is the joint frequency of alleles A and B on the same haplotype. Linkage disequilibrium will be tested using a chi-square test. To limit the number of comparisons, LD analysis will be conducted only on markers within the same gene, or gene region.

Linkage Disequilibrium analysis will be conducted in the White subjects sub-population. LD in other subgroups of subjects may be investigated, as appropriate.

Pairwise LD in the form of r^2 (the squared correlation of genotypes of each pairwise SNP combination) will be calculated for SNPs of interest.

10.4. Ancestry Estimates

Genetic ancestry estimates will be obtained by principal component analysis using EIGENSOFT version 2.0 BETA software package

(http://genepath.med.harvard.edu/~reich/Software.htm). Genetic data of all PGx subjects who passed QC from clinical studies, VEG102616, VEG105192 and VEG107769, will be seeded with genetic data from HapMap subjects which includes 60 Yorubans, 60 Caucasians and 90 Asians (45 from China and 45 from Japan). Diallelic autosomal SNPs from the GWAS in common with SNPs from HapMap Release 23 will be used. Plots will be created using the principle components overlaid with self-reported ethnic groups to aid in visualization of the data clustering and to determine the number of principal components required to infer genetic ancestry [Campbell, 2005]. The plots will be visually inspected to determine if modification of sub-groups, as outlined above, is warranted.

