10.5. Evaluation of Genotypic Association

Logistic regression will be used to examine the effect of marker genotypes on the casecontrol status for diarrhoea (See Section 2.2 for diarrhoea case-control status definition). Prior to the PGx analysis, a model which includes necessary non-genetic independent variables that may influence the endpoints will be identified using the PGx Analysis Population (see Section 7.2 for the covariates that will be evaluated). The model may be reduced, if needed, to include only significantly predictive non-genetic terms (p<0.05) prior to beginning the genetic analyses. Multiple analyses will be run, evaluating each genetic marker, one at a time, while keeping covariates used constant throughout all analyses.

Proportional odds model, adjusting for some of the covariates, will be used to explore the effect of selected or all markers' genotypes on the ordinal diarrhoea toxicity grade levels if it is necessary. One hundred fifty one subjects classified as grade G1 diarrhoea toxicity level that are excluded in case-control analysis will be included in this analysis. The expected number of subjects in this analysis, by grade, is: 132 G0, 151 G1, and 90 G2-G4 (combined) subjects. The proportional odds assumption will be evaluated for the resulting three levels of diarrhoea toxicity. The analyses will be performed using ordinal logistic regression.

The following model will be fitted to identify the genetic effect.

Endpoint = PC1 + PC2 + ... PCn + Covariates + Genotype -- model (1)

The endpoint variables are those listed in Section 7.1. Covariates are those listed in Section 7.2. PC1 represents the first principal component based on the analysis of genome-wide markers, PC2 represents the second principal component and so on. The number of principal components necessary to characterize subject ancestry, n, will be analytically determined; for many datasets an n of 2 or 3 is adequate. An additive genetic model is used here. *Genotype* codes for the number of copies (0, 1, or 2) of the minor (less frequent) allele and will be evaluated as a numeric variable.

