13. APPENDIX

13.1. Diarrhoea PGx Candidate Gene List

Table 13-1 Diarrhoea PGx Candidate Gene List

Gene group	Gene Name	Gene region (NCBI36)	Functional Marker	Numbers of functional markers (Tier 1)	Numbers SNPs/gene (Tier 1 and 2)
Pazopanib's mode of action	FLT1	Chr13: 27,774,389-27,967,265	rs111458691	1	98
	KDR	Chr4: 55,639,406-55,686,519	rs2071559 rs2305948 rs1870377 rs34231037	4	41
	FLT4	Chr5: 179,961,112-180,009,230	rs307826	1	41
	PDGFRA	chr4:54,790,021-54,859,169	rs1800812	1	21
	PDGFRB	chr5:149,473,595-149,515,615			51
	KIT	chr4:55,218,852-55,301,638			55
	VEGFA	chr6:43,845,931-43,862,201	rs699947 rs833061 rs1570360 rs2010963 rs3025039	5	18
Pazopanib ADME	CYP3A4	chr7:99,192,540-99,219,744	rs2740574	1	38
	CYP3A5	chr7:99083749-99115557	rs776746	1	42
	CYP2C8	chr10:96,786,519-96,819,244	rs10509681 rs11572103 rs1058930	3	62
	NR112	chr3:120,984,247-121,020,022	rs3814055	1	83
	ABCB1	chr7:86,970,884-87,180,500	rs1128503 rs2032582 rs1045642	3	204
	ABCG2	Chr4:89,230,440-89,299,035	rs2231137 rs2231142 rs72552713	3	67

				-/	
	SLC6A4	chr17:25,549,032-25,586,841	rs25531 rs1042173	2	17
	IL10	chr1:205,007,571-205,012,462	rs1800896 rs1800872 rs1800871	3	14
	CFTR	chr7:116,907,253-117,095,954	rs73717525	1	50
	CLCA1	chr1:86,706,983-86,738,562			33
	SLC12A2	chr5:127,447,382-127,553,279			23
	ATP1A1	chr1:116,717,359-116,748,919			17
		abr2,24,005,542,24,005,550			27
l genes	ADCY3 ADCY6	chr12:24,895,542-24,995,559 chr12:47,446,242-47,464,144	rs3730071	1	30 9
	NOS3	chr7:150,319,080-150,342,609	RS2070744 RS1799983	2	21
	SLC9A3	chr5:526,425-577,447			31
	SLC5A1	chr22:30,769,259-30,836,645			27
	SLC26A3	chr7:107,193,148-107,230,914			22
ate		chr12:6 326 274 6 254 076	rs2228576	2	15
rel	SCNN1D	chr14,22,221,002,22,200,121	rc27E0224	Z	15
Diarrhoea	SCININIB		153759324		21
	SCNN1G	chr16:23,101,541-23,135,701			24
	ANO1	Chr11:69,602,294-69,713,282			57
	TNF	chr6:31,651,329-31,654,091	rs1800629 rs361525	2	28
	IFNG	chr12:66,834,817-66,839,788	rs2069727 rs2069707	2	12
	IL1B	chr2:113,303,808-113,310,827	RS16944 rs1143627	2	11
	IL4	chr5:132,037,272-132,046,267	rs2243250 rs2070874	2	18
	IL6	chr7:22,733,323-22,738,145	RS1800795 RS1800796 RS10499563	3	24
	IL8	chr4:74,825,139-74,828,297	rs4073 rs1126647	2	7
	IL12A IL12B	chr3:161,189,323-161,196,500 chr5:158,674,369-158,690,059	rs3212227 rs568408	2	12 12
	IL13	chr5:132,021,764-132,024,700	rs1881457 rs1800925 rs20541	3	12
Total				53	1380

 Table 13-2
 Diarrhoea PGx Candidate Gene List (continued)

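### Ancestry PCs are computed from SNPs not thinned for LD and with no check of loadings, so if three or more are kept, PC3 can reflect one large LD block instead of ancestry

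*SAP*

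**What the plan says.** Section 10.4 pools the trial subjects who passed QC with 210 HapMap subjects from three continental groups and runs the principal component analysis in EIGENSOFT. The SNP set is stated outright: "Diallelic autosomal SNPs from the GWAS in common with SNPs from HapMap Release 23 will be used". No r² limit, thinning step, excluded region or loading check follows.

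LD is used elsewhere in the SAP, but not here. Section 10.3 describes pairwise LD within genes, Section 7.6 uses LD for an effective number of tests, and Section 10.5.1 shows it in regional plots.

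Model (1) in Section 10.5 enters PC1 to PCn for every marker. On n, Section 10.5 says "The number of principal components necessary to characterize subject ancestry, n, will be analytically determined" and adds that "for many datasets an n of 2 or 3 is adequate". Section 10.4 instead uses plots overlaid with self-reported ethnic group "to determine the number of principal components required to infer genetic ancestry".

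**The concern.** In an unthinned set, a long run of strongly correlated SNPs acts as one heavily weighted variable and can produce its own component. With three continental groups seeded in, PC1 and PC2 are spent on continental separation. PC3 is therefore the first place where structure among White patients can appear, and also the first place where a block can intrude. Section 10.5 contemplates a third component.

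Two things follow if a block takes PC3 and PC3 is retained:

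- Any marker correlated with the block is partly adjusted for itself and loses power.
- The within-European axis moves to PC4 and drops out of the model when n = 3.

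**Working it through.** **Inputs from the SAP.** PGx total 397 (Table 3-1); HapMap seed 60 + 60 + 90 = 210, so N = 607; 90 cases and 132 controls (Section 5.1); 53 Tier 1 markers and family-wise error 0.05 split over three tiers (Section 7.6); about 1M markers on the chip (Section 7.6).

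**Assumptions, since the SAP gives no figures.** About 60,000 independent SNPs or signals; about 88% of patients European; within-European Fst from 0 to 0.002; one block whose SNPs each have r² 0.5 with a common core. Simulation B also assumes 800,000 shared SNPs.

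**Stated figure reproduced.** 0.05 / 3 / 53 = 3.145 × 10⁻⁴, which agrees with the 3.1 × 10⁻⁴ in Section 5.1.

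**Which component is PC3?** Three separate simulations, one run per setting:

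| Block share of SNP set | Simulation | Block takes PC3 at Fst | R² of PC3 with block |
|---|---|---|---|
| 0.025% (200 of 800,000) | B | none | – |
| 0.0625% (500) | B | 0 and 0.0005 | 0.61, 0.51 |
| 0.1% | A, C | 0.0005 only | – |
| 0.125% (1,000) | B | 0, 0.0005, 0.001 | 0.92 |
| 0.125% | C | 0.001 | 0.87 |
| 0.2% | A, C | 0.0005, 0.001 | 0.97, 0.96 (C) |
| 0.5% | A, C | 0.0005, 0.001, 0.002 | 0.98–1.00 (A), 0.99 (C) |
| 1% | A | 0.0005, 0.001, 0.002 | 0.98–1.00 |

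At Fst 0.002, blocks of 0.2% or less did not take PC3. In B, PC3 was then the ancestry axis (R² 0.97–0.98).

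Without a block, PC3 was the within-European axis in A (R² 0.68–0.98) and C (0.71, 0.93, 0.98). In B at Fst 0.0005, no ancestry axis was recovered among the first five components even with a negligible block, so there was nothing to displace. At Fst 0.001 with the 1,000-SNP block, the axis moved to PC4 (R² 0.93). With the block thinned to 2 SNPs, the R² of PC3 with the block was 0.00–0.01.

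**Power cost.** The non-centrality for 80% power is (3.603 + 0.842)² = 19.76. Adjusting for a component with squared correlation r² to the marker multiplies it by (1 − r²). Power ≈ Φ(√[19.76(1 − r²)] − z), with z = 3.603 for the Tier 1 threshold and 1.960 for p ≤ 0.05.

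| r² | Non-centrality | Square root | Power at 3.1 × 10⁻⁴ | Power at 0.05 |
|---|---|---|---|---|
| 0.2 | 15.81 | 3.976 | 65% | 98% |
| 0.3 | 13.83 | 3.719 | 55% | 96% |
| 0.5 | 9.88 | 3.143 | 32% | 88% |
| 0.9 | 1.98 | 1.406 | 1% | 29% |

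Simulated logistic tests with 90 cases and 132 controls fell from 86–87% to 72%, 63% and 39% at r² 0.2, 0.3 and 0.5.

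**Cost of losing the within-European axis.** Assume a 20-point case-control difference in ancestry. The mean 1-df statistic becomes 1 + (4 × 0.2² × Fst) / (1/90 + 1/132) = 1 + 0.16 × Fst / 0.01869. That is 1.017 at Fst 0.002 and 1.009 at Fst 0.001.

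**Scale against the candidate list.** On a chip of about 1M markers, 0.1–0.2% is 1,000–2,000 SNPs and 0.5% is 5,000. Table 13-1 lists 28 SNPs for TNF (0.003%), 204 for ABCB1, the largest (0.02%), and 1,380 over all 38 genes (0.14%). At the densities of ABCB1 (204 in about 210 kb) and CFTR (50 in about 189 kb), 1,000 SNPs span roughly 1–4 Mb.

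**The case against.** The strongest reply is that the harm needs several conditions together: n of 3 or more, a block far larger than any candidate gene, and weak within-European structure. None is established by the SAP, and each simulated setting was run once. This stands, and it is why the point concerns what can happen.

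A reader might infer that TNF is directly exposed because of its position, "chr6:31,651,329-31,654,091". The SAP gives only those coordinates and a count of 28 SNPs. It says nothing about the extent of LD there, and no correlation between a TNF marker and any component can be derived from it.

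A reader might also infer that the rule for n is bound to accept a block component as real. That is not supported: the analytic rule is unspecified, and the plots against self-reported ethnicity could reveal a component unrelated to ancestry. However, nothing tells the analyst to look at loadings or to drop such a component.

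The remaining replies stand in part:

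- Tier 1 markers at p ≤ 0.05 are still summarised as suggestive (Section 7.6), so at r² up to 0.5 an affected marker would usually still be reported. At r² near 0.9 it would not.
- The power loss is confined to markers correlated with the block, the displaced axis costs little on average, and all analyses are exploratory.
- The earlier documents cited in Section 10.1 are not at hand. The SAP cites them for genotype data and QC, not for the choice of SNPs for the component analysis.

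**Conclusion.** The point holds as a conditional weakness in a stated method. With three or more components retained, a block of about 0.1–0.2% or more of the SNP set can take PC3 when within-European Fst is about 0.001 or less; at Fst 0.002 it takes about 0.5%. Markers correlated with that component then lose power at the Tier 1 threshold, from 80% to 65%, 55% or 32% at r² 0.2, 0.3 or 0.5. When n = 3 the within-European axis may be omitted, at small average cost.

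With n = 2 there is no loss. No particular candidate gene is shown to be exposed, and most markers would be unaffected. Block size, shared-SNP count, Fst and ancestry mix are all assumed. This is a worthwhile improvement at almost no cost, not a threat to the analysis as a whole.

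**What to change.** Amend Section 10.4 to say that:

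- the shared SNPs are thinned for LD before the principal component analysis, for example to pairwise r² < 0.2 in sliding windows;
- the SNP loadings of each component considered for model (1) are inspected;
- a component whose loadings concentrate in one genomic region is not used as an ancestry covariate.

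Excluding all 38 candidate gene regions from the component analysis is optional and not required. The cost is a few lines of text, one filtering step before the planned EIGENSOFT run and a look at the loadings. No new data are needed. The rule should be fixed before association results are seen.

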10.5. Evaluation of Genotypic Association

Logistic regression will be used to examine the effect of marker genotypes on the casecontrol status for diarrhoea (See Section 2.2 for diarrhoea case-control status definition). Prior to the PGx analysis, a model which includes necessary non-genetic independent variables that may influence the endpoints will be identified using the PGx Analysis Population (see Section 7.2 for the covariates that will be evaluated). The model may be reduced, if needed, to include only significantly predictive non-genetic terms (p<0.05) prior to beginning the genetic analyses. Multiple analyses will be run, evaluating each genetic marker, one at a time, while keeping covariates used constant throughout all analyses.

Proportional odds model, adjusting for some of the covariates, will be used to explore the effect of selected or all markers' genotypes on the ordinal diarrhoea toxicity grade levels if it is necessary. One hundred fifty one subjects classified as grade G1 diarrhoea toxicity level that are excluded in case-control analysis will be included in this analysis. The expected number of subjects in this analysis, by grade, is: 132 G0, 151 G1, and 90 G2-G4 (combined) subjects. The proportional odds assumption will be evaluated for the resulting three levels of diarrhoea toxicity. The analyses will be performed using ordinal logistic regression.

The following model will be fitted to identify the genetic effect.

Endpoint = PC1 + PC2 + ... PCn + Covariates + Genotype -- model (1)

The endpoint variables are those listed in Section 7.1. Covariates are those listed in Section 7.2. PC1 represents the first principal component based on the analysis of genome-wide markers, PC2 represents the second principal component and so on. The number of principal components necessary to characterize subject ancestry, n, will be analytically determined; for many datasets an n of 2 or 3 is adequate. An additive genetic model is used here. *Genotype* codes for the number of copies (0, 1, or 2) of the minor (less frequent) allele and will be evaluated as a numeric variable.

